2.3 Rationale for Selected Patients

2.3.1 Precision medicine strategies for optimizing the study population.

This proposal employs two precision medicine strategies: selecting patients with demonstrated WM impairment and limiting recruitment to patients early in their course of illness. Enriching for PFC signaling deficits: D1R/D5R agonists are targeted for SCZ because in these patients, deficits in dopamine release and compensatory upregulation of D1R/D5Rs are associated with WM impairments (23-25). Thus, to formally test whether baseline WM impairments are associated

with differential responses to the study drug, all subjects will be measured on the PennCNB letter n-back task at Visit 1. Individual performance on this task can be compared with drug response during analysis. Illness Phase Specificity: As noted earlier, D1R/D5R agonists enhance inhibitory tuning of PFC pyramidal neurons (32), reducing aberrant cortical functional connectivity, i.e., suppressing "noise." We have previously hypothesized that drugs that have this effect may be relatively more efficacious early in the course of schizophrenia (22), when deficits in inhibitory tuning of PFC pyramidal neurons may be at its most prominent. Further, we had suggested that drugs that attenuate functional connectivity would lose their efficacy in chronic illness because these drugs would exacerbate the damaging impact on network function of illness progression-related loss of gray/white matter and synaptic connectivity (16, 50-53). This hypothesis is supported by early course schizophrenia studies that reported resting-state fMRI (rs-fMRI) functional hyperconnectivity relative to later illness stages (14, 15). Importantly, focusing on the early course illness period reduces the impact of progressive synaptic loss due to advancing illness and the possible cumulative and complex impact of antipsychotic treatment. The notion that drugs that enhance inhibitory tuning might work preferentially early in the course of SCZ is supported by findings with an mGluR2 agonist, which ameliorates symptoms at moderate doses in early course patients (≤3 yr), but which worsens symptoms at high doses in chronic (>10 yr) schizophrenia patients (54).

2.4 Rationale for Dose Selection/Regimen

The trial is set up to have 5 treatment visits, each with single dosing followed by an fMRI scan timed to be at peak blood levels of CVL-562. Subjects will be randomized to the order of doses of CVL-562 (1 mg, 4 mg, 15 mg, or 25 mg, all immediate release formulation) or placebo for the next 5 visits. The randomization will assign 75% of patients to the highest dose on the last visit and 25% would receive the highest dose on one of the other four visits. Only the highest dose (25 mg) will be subject to this pseudo-randomization strategy; all other doses will be randomly distributed. This randomization strategy is intended to minimize the impact on study completion of the association of the 25 mg dose with nausea in approximately 30% of subjects, which may unblind subjects and lead to study discontinuation. The particular doses have been chosen based on prior work using this drug, and in order for the group to have a range of doses to chart a purported 'inverted-U' curve of drug dosing with respect to impact on cognitive functioning. The 1 mg dose has been included in order to catch those participants who are the most sensitive to D1 partial agonism. As we intend to chart the full dose-response for each participant, the selected doses will allow us to catch those participants who are either more or less sensitive to D1 partial agonism, as well as chart differential pharmacodynamics curves. The randomization of dose order will also allow for separation of practice effects, and we can test to ensure that drug effects are stronger than practice effects. As the timing of CVL-562's effects is >30% delayed during a fed state than during a fasting state (per investigator's brochure) we will offer a small meal to those who have not eaten a meal within two hours

prior to the visit start. This is an attempt to achieve a fed state across all participants, and achieve standard pharmacokinetics during the scan.

3. STATEMENT OF PURPOSE/OBJECTIVES

This U01 study is a response to the NIMH Program Announcement for National Cooperative Drug Development Groups (NCDDG) intended to accelerate the development of a high priority therapeutic agent by establishing its dose-related pharmacodynamic effects on biomarkers designed to inform subsequent clinical development. The overall aim is to establish neuroimaging biomarkers of D1R/D5R target engagement to accelerate development of D1R/D5R agonists in humans to treat cognitive impairments that underlie functional disability in schizophrenia, a key unaddressed clinical and public health concern.

3.1 Primary Endpoint

To test if CVL-562 has dose-related effects in schizophrenia patients on putative neural biomarkers of D1R/D5R stimulation. We will examine the dose-specific effects of CVL-562 on blood oxygen level dependent (BOLD) signal change during working memory procedures. The primary outcome measure is an analysis of variance of the dose-dependent effects of CVL-562 on the blood oxygen level dependent signal (BOLD) during spatial working memory. Post-hoc univariate tests will quantify directional dose-related CVL-562 effects.

3.2 Secondary Endpoint 1

To test in how many participants CVL-562 produces a dose-related modulation of BOLD signal during working memory procedures.

3.3 Secondary Endpoint 2

To test if CVL-562 produces a dose-related modulation of sWM behavioral performance collected during fMRI. This will be examined using the behavioral data generated during neuroimaging to quantify dose-related CVL-562 effects on sWM performance both with and without distractors.

3.4 Secondary Endpoint 3

We plan to directly examine the association between trial-by-trial sWM performance and task-evoked BOLD signal by regressing trial-by-trial sWM performance with and without distractors with the relevant BOLD signal.

3.5 Secondary Endpoint 4

We will examine the dose-dependent effects of CVL-562 on the functional connectivity of brain regions during spatial working memory.

3.6 Secondary Endpoint 5

We will examine the dose-dependent effects of CVL-562 on the resting state functional connectivity using a data-driven global brain connectivity (GBC) metric.

3.7 Secondary Endpoint 6

We will compare the change in resting state GBC as a function of CVL-562 dose with the transcriptomic maps from the Allen Human Brain Atlas relevant to risk genes in schizophrenia.

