administration produced 12 hours of clinical improvement (35). It was developed by Pfizer, Inc. and recently acquired by Cerevel Therapeutics, who have agreed to support the proposed trial. As noted above, CVL-562, like all prior pro-cognitive D1R agonists, also stimulates D5R. D5Rs are located on proximal dendrites, while D1Rs are located on dendritic spines and distal dendrites (38). D5R, like D1R, plays an important role in sWM (39). We are taking several steps in this study to address potential implications of the dual actions of CVL-562. First, we are densely mapping the dose-response curve for CVL-562 from marginal occupancy to the limits of tolerability to determine whether there are non-linear (inverted-U) doserelated effects. The moderate intrinsic activity of CVL-562 at D1R may protect against detrimental effects of cognition related to overstimulation of D1R and direct impairment of cognition was not observed in the Pfizer Phase IB SCZ trial. However, it is still possible that this drug produces detrimental effects on cognition (inverted-U dose-response) at given doses due to overstimulation of D5R. Therefore, our study design incorporates a wide range of doses to identify individual responses to each dose and allow us to map individual pharmacologic dose-response profiles.

2.2.4 Ability of responses to single doses to predict the effects of chronic dosing.

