All preprocessing of imaging data will follow Human Connectome Project (HCP) pipelines(67). For each CIFTI-based gray-ordinate, least-squares coefficients will be generated independently reflecting BOLD signal during task conditions. We will use a general linear model to fit the hemodynamic response function (HRF) using a finite impulse response function (FIR) for the timepoints covering the encoding (timepoints 1-2) and delay epochs (timepoints 3-14) and the natural decay in the HRF (timepoints 15-20). Assessing the HRF across these 20 timepoints for each task condition (motor, spatial working memory, distractionnear and distraction-far) will allow us to examine the effects of dose response across our epochs of interest. From these general linear models, we will form within-subject contrasts for second-level analyses. We will use non-parametric combination (NPC) to examine the multivariate effects of dose (5 levels) and task condition (motor, spatial working memory, distraction-near and distraction-far) at each timepoint within each voxel of an independently defined mask of spatial working memory regions from the prior work of [name] (co-investigator). When compared with an ANOVA or related MANOVA, NPC provides a more statistically efficient and robust approach for this primary endpoint, while still allowing for testing of dose-dependent effects of drug on the task BOLD signal at different timepoints(68). NPC has the additional advantage of accommodating the multivariate and potentially non-normally distributed nature of our endpoints. Furthermore, NPC maintains better power at fixed sample sizes than traditional multivariate tests, which have increasing power as the number of modalities increases, until an inflection point, after which traditional test power declines. Significant voxels will be determined using non-parametric statistics and corrections for multiple comparisons as appropriate.

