We will test if CVL-562 produces a dose-related modulation of sWM performance. We will leverage behavioral data generated during neuroimaging to quantify dose-related CVL-562 effects on sWM performance and also on sWM performance with distraction. Here, the outcome measure will be the sWM performance measured as the angular difference between the target presentation and the participant's response. We will conduct a 4 (task condition--motor, spatial working memory, near-distraction, far-distraction) x 5 (dose) repeated measures ANOVA. Post-hoc analyses will be conducted to demonstrate the directional effects of behavioral performance with respect to dosing. All statistics will be corrected for multiple

comparisons.

10.1.4 Secondary Endpoint 3

We will directly examine the association between sWM performance and task-evoked BOLD signal. An analysis of variance of the dose-dependent effects of CVL-562 on the task-evoked BOLD signal will be conducted as described for the Primary Endpoint, but instead will use the trial-by-trial regressor of sWM performance as a covariate. sWM performance will be measured as described in Secondary Endpoint 2, and will be treated as a covariate of interest in the above-specified general linear model. An effect of a 5 (drug dose) x 4 (task condition) interaction with the sWM precision covariate would indicate that the drug has an effect of BOLD signal change that is specifically associated with a change in trial-by-trial sWM performance.

10.1.5 Secondary Endpoint 4

We will conduct an analysis of variance of the dose-dependent effects of CVL-562 on the functional connectivity of brain regions during spatial working memory. In contrast to the task-evoked modeling, here we will use 'time point' selection methods to isolate specific time points during the delay period of each trial, which we will combine into a time series. This BOLD signal will be used to co-vary a given region of interest with the rest of the brain. Given prior work by our team we will focus on the fronto-parietal control network (FPCN) as a 'seed' region for this task-evoked FC analysis. Specifically, we will quantify covariation of the extracted FPCN signals with all other CIFTI greyordinates. This index of FPCN 'functional integrity' will be obtained across sWM conditions and CVL-562 doses for each subject and will then be entered into 2nd-level random effect analyses.

10.1.6 Secondary Endpoint 5

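### The doses were chosen to chart an inverted U, but no specified analysis tests for a downturn, and every 25 mg comparison is confounded with visit order

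*Combined protocol and SAP*

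**What the plan says.** Section 2.2.3 says the dose-response curve is mapped densely "to determine whether there are non-linear (inverted-U) doserelated effects". Section 2.4 says the doses give a range with which to "chart a purported 'inverted-U' curve of drug dosing with respect to impact on cognitive functioning".

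The analysis text does not follow this through to a test of shape:

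- Section 3.1: "The primary outcome measure is an analysis of variance of the dose-dependent effects of CVL-562" on BOLD signal, followed by "Post-hoc univariate tests will quantify directional dose-related CVL-562 effects". No dose pair, trend or shape is named.
- Section 10.1.1: non-parametric combination (NPC) is used "to examine the multivariate effects of dose (5 levels) and task condition" at each timepoint and voxel. Power rests on combined partial t-tests that are not defined. This section names no post-hoc test.
- Section 10.1.2: a binary responder outcome per participant, with no shape attached.
- Section 10.1.3: a 4 (task condition) by 5 (dose) repeated-measures ANOVA of working-memory error. Then: "Post-hoc analyses will be conducted to demonstrate the directional effects of behavioral performance with respect to dosing".
- Section 2.2.5: plasma level is to be explored as a predictor, with no functional form.

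On order, section 4.4 gives 25 mg at the last test visit to 75% of patients and at one of the other four visits to 25%. Section 2.4 says that randomising the order allows practice effects to be separated. Neither 10.1.1 nor 10.1.3 includes a visit or period term.

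**The concern.** A plateau and an inverted U can both produce a significant five-level dose effect. They differ in one respect: whether the response falls again at the higher doses. Answering that needs a comparison between active doses, and the plan commits to none.

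The distinction matters because section 3 says the dose-related effects are meant to inform later development, and section 2.2.2 looks for biomarkers that support go/no-go decisions. A plateau read as a downturn, or a downturn read as a plateau, would carry forward a wrong picture of the dose range.

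Visit order adds to this. The dose on which a downturn claim mainly turns is also the one given last to most patients. Fatigue or declining engagement over visits could imitate a downturn, and practice could hide one.

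**Working it through.** **1. The plan's own figure.** The documents give no power or error figure for dose shape. The only power statement (section 10.1.1) is a detectable effect of 0.18 to 0.37 for 25 to 100 participants at 80% power. A plain two-sided paired t-test gives 0.283 at N = 100 and 0.584 at N = 25, so the stated range does not follow from the stated inputs. It can be reached by averaging k partial tests with common correlation r, using d × √((1 + (k − 1)r)/k). With k = 4 and r = 0.2 the factor is √(1.6/4) = 0.632, giving 0.179 and 0.369. Those values of k and r are not in the documents. The figure is therefore not shown to be wrong, but the partial tests that would reveal whether dose order is used are undefined.

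**2. Reading shape from significance against placebo.** This reading rule is assumed. Suppose the true response is equal at 4, 15 and 25 mg. Each comparison with placebo has z with mean 1.960 + 0.842 = 2.802 (80% power) or 1.960 (50% power). The comparisons share the placebo scan and so correlate 0.5. The pattern of interest is 4 or 15 mg significant and 25 mg not.

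| Power per comparison | P(25 mg not significant) | P(pattern), simulated |
|---|---|---|
| 80% | 20% | 15% |
| 50% | 50% | 25% |

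So when 25 mg misses significance on a true plateau, one of the other two doses is significant in 15/20 = 75% or 25/50 = 50% of cases. A direct 25 versus 15 mg contrast at two-sided 0.05 falsely points downward in 2.5%.

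**3. Visit order.** Number the test visits 1 to 5 and assume the 25% are spread equally over visits 1 to 4.

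- Mean position of 25 mg: 0.75 × 5 + 0.25 × (1 + 2 + 3 + 4)/4 = 3.75 + 0.625 = 4.375.
- Mean position of each other treatment: (15 − 4.375)/4 = 2.656.
- Difference: 4.375 − 2.656 = 1.719.

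Without a visit term, a linear change of b per visit adds about 1.72b to 25 mg minus any other single treatment. For the mean of 15 and 25 mg against 4 mg it adds half of that, 0.86b.

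**4. What a direct downturn contrast can detect.** Suppose peak versus placebo has 80% power (mean z 2.802) and half the effect is lost at 25 mg. The peak versus 25 mg contrast then has mean z 1.401 and power of about 29%. If instead the overall 4-df dose test is set at 80% power for a 15 mg peak with half lost at 25 mg (peak d_z = 0.326, N = 100), the contrast has 37%. If the whole effect is lost, power is 81% to 83%. All are before multiplicity or visit adjustment.

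**The case against.** The best defence is that the plan is silent on shape without being wrong. The primary objective asks only for dose-related effects on BOLD. Section 2.4 ties the inverted U to cognition, and section 2.2.3 treats it as a possibility. Directional post-hoc tests could include 15 versus 25 mg. Both sections also stress individual curves, which group contrasts need not match. This stands as far as it goes: no analysis rules out a downturn test. But none commits to one either, and a contrast chosen after seeing the dose means is weaker evidence. The cognition point makes the gap most direct in 10.1.3, where the five-level ANOVA is explicit.

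Three stronger readings are tempting and are not supported.

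- *Dose is declared unordered.* The documents say five levels. The undefined partial tests could be ordered contrasts.
- *The primary analysis loses a known amount of power.* For a single outcome, an effect with 80% power on a perfectly matched 1-df contrast has about 60% on a 4-df F test, and a realistic five-shape contrast set gains about 8 to 12 points over the F test. Section 10.1.1 specifies voxelwise NPC, saying "When compared with an ANOVA or related MANOVA, NPC provides a more statistically efficient and robust approach for this primary endpoint", and nothing can be computed for it without the partial tests and their correlation. The overall test also keeps power against an inverted U, whereas a linear trend alone can fall to 5% to 16% for some such shapes.
- *The trial cannot control error.* Section 10.1.3 promises multiplicity correction of all statistics and 10.1.1 promises it as appropriate. What is missing is the family of tests to which the correction applies.

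It is also fair that no passage states the reading rule in step 2. Requiring a significant overall test first gives about 14% to 17% with uncorrected comparisons, and 21% to 24% with Bonferroni, so neither safeguard removes the problem if that rule were used.

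**Conclusion.** The point holds as a gap between the stated reason for the dose range and the specified analysis. No specified test separates a plateau from a downturn, and the dose models omit visit although the randomisation ties 25 mg to the last one. The visit-order point is the firmer of the two: if there is a linear per-visit effect, following sections 10.1.1 and 10.1.3 as written biases a 25 mg comparison with another treatment by about 1.72 times that effect. This assumes an equal spread of the remaining 25%; the size and direction of any visit effect are unknown. The 15% to 25% figure depends on an assumed reading rule and an exactly flat curve, and shows what unplanned reading of shape could cost. The defect concerns inference on shape and bias at 25 mg. Whether a dose effect can be detected at all is a separate matter.

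**What to change.** Keep the overall dose test and change the analysis text as follows.

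1. Add test-visit number to the dose models in 10.1.1 and 10.1.3.
2. Replace the unnamed post-hoc tests in 3.1 and 10.1.3 with a small pre-specified set: a monotone trend, an inverted-U contrast, and two downturn contrasts (25 mg versus 15 mg, and the mean of 15 and 25 mg versus 4 mg). The second is needed because 25 versus 15 mg misses a 4 mg peak that has already fallen by 15 mg. In 10.1.1, define the NPC partial tests accordingly or add the set as a follow-up. Fix the sign of benefit for each outcome and the dose scale.
3. Control the set jointly by max-T permutation, adjusted for visit, with dose orders permuted under the actual 75/25 allocation rule.
4. Claim an inverted U only if a downturn contrast is significant. Otherwise report the contrast with its confidence interval and call the shape unresolved.
5. Reconcile the ANOVA in 3.1 with the NPC in 10.1.1.

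This changes no patient, visit or dose. The costs are statistical. Power for a partial downturn is roughly 30% to 37% in the cases of step 4, before adjustment, so unresolved will be a common answer. The contrasts are less sensitive to a single-dose spike or a 1 mg peak, which is why the overall test stays. Visit adjustment also widens the 25 mg contrasts: in a simulated allocation of 100, the variance of 25 versus 15 mg rose about 1.55-fold with visit as a five-level factor. A linear visit term costs less but removes only linear drift.

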3.8 Exploratory Endpoint

We will conduct exploratory analyses to test whether genetic variants of genes related to dopamine or CVL-562 metabolism relate to changes in BOLD signal in response to CVL-562.

4. STUDY PLAN AND PROCEDURES

4.1 Study Design Overview

Patients (n=120) will be recruited from four centers experienced in recruiting and enrolling patients with early episode psychosis into research (Columbia University/RFMH, SUNY Stony Brook, University of Pennsylvania, Yale University). Patients will be recruited over a total of 2-3 years. Study participation for patients will last approximately one-two months. After an initial phone screen to determine interest and general eligibility, participants will be scheduled for an in-person assessment to confirm full eligibility. Study procedures will be reviewed with the participant, and written consent will be obtained upon arrival during this visit.

Upon successfully completing the screening evaluations, all eligible subjects will complete 7 total study visits (of which some may be spread over multiple days), 5 of which will be test visits involving the administration of CVL-562 or placebo (Figure 1). Each test visit will be separated by at least 48 hours (six half-lives of CVL-562, per investigator brochure from Pfizer/Cerevel the half-life is 7.5 hours). Given the repeated visits required in this study, participants will be offered an elective inpatient admission on a research psychiatric unit, if space is available, for further observation or isolation (due to COVID-19 exposure risk) as needed. For those requiring housing, a stay at a nearby hotel will be offered. The baseline visit will involve informed consent and screening assessments to determine eligibility, including a structured clinical interview (SCID-V), Penn Reading Assessment (PRA), Edinburgh Handedness Inventory, PANSS, PennCNB letter n-back task, Calgary Depression Scale for Schizophrenia, spatial working

memory task, practice flashing checkerboard task, Beck Anxiety Inventory, Columbia-Suicide Severity Rating Scale—baseline/screening (C-SSRS, baseline/screening), urine toxicology/pregnancy, baseline bloodwork (complete blood count (CBC) with differential, comprehensive metabolic panel (CMP), Hepatitis B, Hepatitis C, HIV, genetics (optional)), EKG, vital signs, health history, physical exam, assessment and an optional mock scanner experience. Preexisting health information may be used to determine eligibility if it was obtained within 3 weeks prior to the date of consent. Subjects will be randomized to the order of doses of CVL-562 (1 mg, 4 mg, 15 mg, or 25 mg, immediate release formulation) or placebo for the next 5 visits. The randomization will assign 75% of patients to the highest dose on the last visit and 25% will receive the highest dose on one of the other four visits. Only the highest dose will be subject to this pseudo-randomization strategy. This is intended to minimize the impact on study completion of the association of the 25 mg dose with nausea in approximately 30% of subjects, which might unblind subjects and lead to study discontinuation. All other dosing will be randomly distributed. All female participants will be required to be on birth control (or abstinence) and will receive pregnancy tests at the start of each study visit. Information on nicotine use, the amount and duration of use will be collected at the start of the study using the Fagerstrom Test for Nicotine Dependence Questionnaire. All subjects will be tested for COVID-19 as part of Visit 1. COVID-19 testing may be repeated after Visit 1 based on symptoms.

Each treatment visit will begin with clinical assessments required to continue on this study. These assessments include urine sample for toxicology/pregnancy exam, Positive and Negative Syndrome Scale (PANSS), Columbia-Suicide Severity Rating Scale—since last visit (C-SSRS, since last visit), MRI safety assessment, and vital signs. A lifestyle questionnaire will be administered to understand basic events that occurred in the hours before the scan, including how much caffeine was used, how much food was eaten, pain levels and whether nicotine was used. If participants have not had a meal within two hours prior to the start of the study visit, they will be offered a small meal to induce a fed state, as the timing of the study drug's effects have a different timeline during a fed vs. fasting state. A brief refresher session on the spatial working memory task will be presented to the participants to remind them of the task instructions, at this point or after drug administration prior to the start of scanning. Following this, the treatment visit medication will be administered and the subject will enter the fMRI scanner to perform the spatial working memory task. Vital signs will be taken before drug administration and prior to and after scanning. Scanning will be timed to have imaging coincide with peak CVL-562 plasma levels, i.e., it will begin approximately 75 minutes following medication administration and last for approximately 90 minutes (up to 2 hours). Plasma levels of CVL-562 will be obtained prior to and following imaging with a blood draw from either venipuncture or an IV continued with a slow rate of normal saline infused during the scan (20 mL/hour) to minimize needlesticks. The slow rate of normal saline is used to keep the IV open during the scan, and prevent clotting in the IV. The use of either two venipunctures (one prior to imaging and one following imaging) or a continuous IV will be made after assessing patient preference, and procedure feasibility. Vital signs, PANSS, C-SSRS—since last visit, and PennCNB will be administered immediately following removal from the scanner. All subjects will be observed for at least 2 hours following dosing, and provided follow-up (see below, Protection Against CVL-562 Risks).

After completion of the 5 treatment visits, participants will be scheduled for a followup visit to conduct an exit interview, with debriefing of the study.

[figure not shown]

Figure 1. Overview of Study Design.

4.1.1 4.1.1. Protection Against CVL-562 Risks.

The subject recruitment process entails an effective and rigorous screening, which will exclude any subjects who could be at greater risk for complications because of medical, neurological or psychiatric illnesses. We have successfully employed these stringent screening procedures in all our protocols and have had great success in recruiting subjects who are at low risk for receiving experimental pharmacology (ex: ketamine (55), delta9-tetrahydrocannabinol (43, 56), etc.) and who are likely to tolerate the procedure well. Subjects will be monitored during drug administration by an experienced member of the research team (nurse, coordinator and/or psychiatrist). These team members have experience with pharmacologic imaging, and will provide ongoing support and alleviate concerns for those subjects experiencing side-effects. Furthermore, ondansetron will be available for intravenous or sublingual administration to rapidly control nausea and/or vomiting during scanning if needed. Subjects will be observed for at least 2 hours after dosing. If intolerable physical or behavioral symptoms persist, subjects will be assessed in the emergency room and/or on an inpatient unit depending on the level of severity of symptoms for further observation and overnight, if necessary. Vitals will be assessed prior to drug administration on each test visit, just prior to beginning fMRI scan, and after fMRI scanning finishes. We will also administer the Columbia-Suicide Severity Rating Scale—since last visit (C-SSRS, since last visit) prior to drug administration and after fMRI scanning, though it is important to note that CVL-562 has no known effect on suicidality. Subjects will be

advised NOT to drive to and from the testing sessions, and instead we will arrange alternative means of transportation for all subjects (e.g. taxi). A physician investigator (MD) will approve the discharge of subjects following the completion of each treatment visit. Following discharge from each treatment visit, subjects will be provided a number to call to reach an on-call psychiatrist (24 hours/day) should delayed unpleasant effects occur. Subjects who experience any intolerable effects at any point will not be permitted to continue participation. Please see Section 9.4 for further details on criteria for stopping participation. Post-testing: Contact with participants will be maintained during the study and following its completion. We will contact all subjects approximately 24 hours after drug administration to check for side effects. A final, in-person follow-up visit will occur after the last treatment visit to assess side effects and complete final bloodwork. Furthermore, we will conduct a follow-up call approximately 1 month after study completion (i.e., after the final in-person visit) to assess for late or ongoing adverse effects. Any subjects that experience lingering side effects will be followed by the study team until resolved or stabilized, and then will be directed to follow-up with their primary health care provider. All imaging will occur at sites specifically designed, equipped, and functioning in support of these types of studies, and includes the onsite presence of medical supervision with experienced medical, nursing, research and/or technical staff. Although we do not expect significant problems to occur, if any adverse effects occur during the fMRI session, appropriate treatment will be instituted for symptomatic relief. All sites will implement clear protocols for addressing medical urgencies and emergencies, including, but not limited to, emergent assessment, use of a crash cart, and transportation to the emergency room.

